9.2 Risks and Expected Benefits

There are no anticipated risks related to participation in this study. Per clinical guidelines, all participants in this study should be undergoing lipid screen as part of their standard care. Currently, providers are not alerted via Epic to the need to order this test. The purpose of this study is to determine the most effective way, within Epic, of alerting providers. All eligible pediatric patients, including those initially randomized to the standard of care/control arm, will eventually receive the alert condition determined to have the greatest effect on uptake of ordering by providers and, through them, blood draws facilitated by parents/LARs.

The primary benefit of this study is that we will learn which form of alert, if any, has the greatest impact on uptake of this recommended screening. Notably, Geisinger has committed to implementing whichever alert format turns out to have the greatest impact, thereby creating immediate benefit for all relevant Geisinger patients and their families. This benefit will extent to study participants who were initially randomized to other conditions and who are seen again at Geisinger prior to turning twelve.

The study team will only receive de-identified data to help minimize risk of loss of confidentiality.

9.3 Data Monitoring Plan

Not applicable.

Evaluating the Efficacy of Pediatric Lipid Screening Alerts
(NCT04118348)

Statistical Analysis Plan

October 13, 2023

Statistical Analysis Plan

Note: An earlier document included the study protocol, but this section was removed since this was redundant with an existing protocol (2022-11-10). The current document further updates an interim document to correct some data management errors and specify corrections for multiple comparisons that are more consistent with the original protocol.

As of the writing of this plan, primary and additional analyses have already been completed.

Primary Analyses

Binary logistic generalized linear mixed models (GLMMs) were used to analyze the primary outcomes – lipid screening orders and completions one week after the visit – as a function of condition, with the provider added to the model as a random effect. As the researchers were interested in the comparison between the experimental groups and the control group, as well as the relative effectiveness between the experimental groups, they conducted contrasts between all 4 groups using sets of three GLMMs with shifting reference categories. Post hoc pairwise tests were also run, adjusting for multiple comparisons using the least significant difference test. Odds ratios (ORs) were calculated, along with 95% confidence intervals (CIs); two-tailed p -values < 0.05 were used to determine statistical significance. To represent effect size, the standardized statistic, Cohen's d , was estimated using the formula $\text{LogOddsRatio} \times \sqrt{3}/\pi$ (Hasselblad & Hedges, 1995). Raw percentages and 95% CIs were also presented.

Additional Analyses

Epic Storyboard (a newly introduced method of showing information to the provider in the EHR) was introduced on November 1, 2019. As Epic Storyboard might have changed the way providers engaged with alerts, the researchers reran the models including an interaction term between the presence of Epic Storyboard (i.e., patient encounters after November 1, 2019) and the conditions.

The same kind of GLMM model as used in the primary analyses was also used to examine the effect of the experimental conditions on completions 6 months after the intervention.

To conduct pre-post comparisons, the researchers examined the records of 12,252 eligible patients with the same kind of visits 6 months prior to the study period. The four experimental conditions were compared against this pre-alert group using the same kind of GLMM used in the primary analyses. All of the contrasts were made against one group, the pre-alert group, so no adjustment was made for multiple comparisons.

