6.5 Procedures

Patients who are eligible for this study will be randomized into one of four groups via an EPIC randomization algorithm run automatically at the time of the visit:

1. Control group (6-month delay before their providers will receive an alert)
2. Health maintenance tab
3. Best practice alert
4. Best practice alert and health maintenance tab

Geisinger Health System will introduce EPIC's Storyboard panel (a novel way of summarizing patient information) approximately one month into this study. The analysis plan will therefore attempt to test for the potential impact of this change.

The providers will be prompted to discuss and order screening lipid study that is non fasting at the time of the visit with the patient, based on the alerts above. Some families will have an alert in their MyGeisinger portal stating that a health maintenance test is due and to discuss with their provider.

The outcomes will be reviewed and classified as followed, for descriptive reporting purposes:

1. Lipid screening ordered
2. Lipid screening ordered and completed
3. Lipid screening ordered but not completed
4. Lipid screening declined with reason why
5. Alert not acted on at all

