6.8 Statistics

6.8.1 Statistical Analysis Plan

Analyses will test whether each of the active alert conditions have a significant impact on the outcomes, relative to the control group, as well as comparing across the BPA-only, HMT-only, and BPA+HMT groups. Interactions between Storyboard implementation in EPIC and the experimental conditions will be tested; if any are significant, further analyses will test whether and how results replicate in the different contexts before and after Storyboard introduction.

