6.8.2 Statistical Power and Sample Size Considerations

As noted in Section 6.2.1, approximately 24,000 patients of age 9-11 are expected to come in for child wellness visits over the course of six months. Allowing for seasonal variations and patients who are ineligible according to study exclusion criteria, we still expect upwards of 18,000 patients over six months, but as noted above we will enroll all eligible participants throughout the study period. Randomly allocated at 4,500 patients per condition, this provides 95% power to detect very small (Cohen's $d=0.076$) mean effect size differences across any two conditions, using a threshold $\alpha=0.05$ for a two-tailed test of statistical significance. Only more moderate effect size differences ($d\geq0.20$) may be detectable in the time period prior to Storyboard implementation, where only around 650 patients are expected per condition.

Another way to conceive of this is if we assume a default screening rate of 1.3% (i.e., 1,238 patients, among 96,944, who had a lipid screen drawn). A sample size of 4,500 per condition allows us to detect a 1% increase in screenings (to 2.3%) with 95% power, using a binomial proportion z-test. A sample size of 650 per condition allows us to detect at least a 3.4% increase in screenings (to 4.7%) with 95% power.

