9 PROTECTION OF HUMAN SUBJECTS

9.1 Informed Consent

We are requesting a waiver of consent and HIPAA authorization for this study. This study imposes only minimal risks on pediatric patient-participants, their providers, and their parents/LARs (see section 9.2).

The purpose of this pragmatic trial is to inform implementation of a new EHR alert by learning how different alert formats (and the standard practice of no alerts at all) affect providers' behavior in ordering pediatric lipid panels and, subsequently, parents'/LARs' facilitation of blood draws for pediatric patients. It is well known that providers suffer from "alert fatigue" and Epic alerts are routinely ignored by providers. Similarly, the fact that a provider noticed an alert does not mean that he or she will act on it, nor does it mean that the patient or their parent/LAR will necessarily comply with the provider's alert-based recommendation. When implemented, alerts are intended to perform automatically, setting off a chain of provider and/or patient/parent behavior without any additional prompting from outside of the EHR system. For the study team to emphasize the presence or absence of a new alert via an informed consent process defeats the

purpose of the study, which is to understand how providers and parents/LARs behave in response to alerts *as they would be implemented universally at Geisinger*. Hence, this study could not practicably be carried out without the requested waivers of consent and HIPAA authorization.

Because the current status quo at Geisinger is no Epic alerts for pediatric lipid screening, temporary randomization to the no-alert condition does not adversely affect those participants' rights or welfare. Conversely, although it is currently the standard of care not to specially alert providers to the need for this test, universal screening is indeed considered best practice in pediatrics. Thus, patients randomized to have their provider alerted that they are eligible for this test, which might prompt a conversation with their parents/LARs about this test, also will not have their rights or welfare adversely affected by this study.

Finally, the alert format shown to have the greatest impact on uptake will quickly be implemented for all pediatric patients' providers.

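### The Storyboard-by-condition interaction compares about the first month of alert availability with the later months, so it confounds any Storyboard effect with any change in the alert effect over time.

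*SAP*

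**What the plan says.** The SAP's primary model is a logistic mixed model with condition as the fixed effect and provider as a random effect. Its section on Additional Analyses raises the possibility that Storyboard altered providers' handling of an alert; to examine this, the analysts "reran the models including an interaction term between the presence of Epic Storyboard (i.e., patient encounters after November 1, 2019) and the conditions". No calendar-time, time-since-launch or cumulative-exposure term is described.

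Protocol 6.5 expects Storyboard "approximately one month into this study" and wants the analysis to examine its possible impact. Protocol 6.8.1 adds that, if an interaction is significant, "further analyses will test whether and how results replicate in the different contexts before and after Storyboard introduction". Protocol 6.8.2 gives the expected numbers: "Randomly allocated at 4,500 patients per condition" for the whole study, and a pre-Storyboard period "where only around 650 patients are expected per condition".

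Protocol 9.1 says that no Epic alert for pediatric lipid screening was in use before the study. In its argument for a consent waiver, it also describes alert fatigue as well known and says that "Epic alerts are routinely ignored by providers".

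**The concern.** Storyboard arrived on one date for the whole system, about a month after the alerts first became available. In the SAP's model, Storyboard status is therefore a step function of time since launch. With no time term and no group left without Storyboard, whatever changes the alert effect between the first month and the later months enters the Storyboard-by-condition coefficient.

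Randomisation protects the comparison of arms within each period. The concurrent control arm also removes secular change in background screening. Neither protects the change in the alert effect from one period to the next, because control patients trigger no alert whose effect could fade. A provider random effect does not remove it either.

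At stake is the interpretation. A fading response would read as Storyboard weakening the alerts, and a growing familiarity would read as Storyboard helping them. A null interaction would not settle the matter, since fading and a helpful Storyboard could cancel. The before/after follow-up in Protocol 6.8.1 has the same confounding. Whether an alert's effect lasts also matters to a health system that intends to roll out the best-performing format.

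**Working it through.** **The plan's own figures.** Protocol 6.8.2 works at 95% power, "using a threshold $\alpha=0.05$ for a two-tailed test of statistical significance". Recomputed:
- d = 0.076, 4,500 per condition: 95.0%.
- d = 0.20, 650 per condition: 95.0%.
- 1.3% versus 2.3%, 4,500 per condition: 94.6%.
- 1.3% versus 4.7%, 650 per condition: 95.0%.

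These reproduce. The timing also agrees: 650/4,500 × 6 months = 0.87 month, close to one month.

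**Inputs from the documents.** Per arm, 650 patients before Storyboard and 4,500 − 650 = 3,850 after; control rate 1.3%; two-sided 0.05.

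**Assumptions, not in the documents.** 31 days before and 151 days after Storyboard, even arrivals within each period, a flat control rate, one alert arm versus control, no provider clustering, and a true Storyboard effect of zero. The alert's log odds ratio (OR) decays exponentially with time constant τ:

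log OR(t) = log OR∞ + (log OR₀ − log OR∞) × exp(−t/τ)

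**Formulas.** With a flat control rate, the interaction is b = logit(alert rate after) − logit(alert rate before). Its SE is √Σ 1/[n p (1 − p)] over the four arm-by-period cells. The chance of significance is Φ(|b|/SE − 1.96) + Φ(−|b|/SE − 1.96).

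**One case in full: OR 4 fading to 1.5, τ = 30 days.**
- Mean alert-arm rate: 3.57% before, 2.08% after.
- OR versus control: 2.81 before, 1.61 after. Ratio = 1.61/2.81 = 0.57, so b = −0.554.
- SE² = 0.0447 (alert, before) + 0.0128 (alert, after) + 0.1199 (control, before) + 0.0202 (control, after) = 0.1976, so SE = 0.44.
- |b|/SE = 1.25. Chance of significance = Φ(−0.71) + Φ(−3.21) = 24%.

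**Range at a 1.3% control rate, no Storyboard effect.**

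| Assumed fading of the alert OR | Ratio of ORs | Chance of p < 0.05 |
|---|---|---|
| None (OR 3 throughout) | 1.00 | 5% |
| 2.6 to 1.4, half-life 60 days | 0.73 | 11% |
| 4 to 2, τ = 30 days | 0.68 | 14% |
| 4 to 1.5, τ = 30 days | 0.57 | 24% |
| 4 to 1.2, τ = 30 days (steeper than the quoted range) | 0.50 | 33% |

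The quoted range of 0.57 to 0.73 is the second to fourth rows. A higher control rate makes false significance more frequent. With even arrivals over six months, OR 4 fading to 2 or to 1.2, and time constants of 0.5 to 2 months, the chance is 12% to 36% at 1.3% and 29% to 86% at an assumed 5%.

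**What a time term recovers.** For OR 4 to 1.5, τ = 30 days, adding time since launch and its interaction with condition gives:

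| Time term | Ratio of ORs at the step (truth 1.00) | SE of log |
|---|---|---|
| None (as in the SAP) | 0.57 | 0.44 |
| Linear | 0.69 | 0.58 |
| Log, as log of (days + 7) | 0.85 | 0.75 |
| Exact decay shape | 1.00 | 0.94 |

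Log time raises the SE by about 70% (0.75/0.44 = 1.70). With the exact shape, which would not be known, the approximate 95% interval is 0.16 to 6.3. The main limit is the pre-Storyboard control cell: 650 × 0.013 = 8.5 expected events.

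**The case against.** The strongest reply is that nothing in the documents shows that this alert's effect faded. Protocol 9.1 mentions alert fatigue in general terms to justify a waiver of consent, and that is equally compatible with a low response from the first day. This stands. The confounding follows from the design, but the misattribution is conditional on a change over time.

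A reader might also infer that the pre-Storyboard window is each provider's own first month with the alerts. It is the first month of availability. A provider whose first alerted patient came after 1 November had no earlier exposure, and the documents give no per-provider data.

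At the planning rate the interaction is imprecise. Even where fading is assumed, most trials (76% to 89% over the quoted range) would show no significant interaction and would not trigger the protocol's follow-up. This also stands, but a non-significant result would not show that Storyboard had no effect.

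A reader might further suspect that the mix of patients differs between the first month and later. The documents give no figure for this, and it would matter only if the alert effect varied with case mix, so the point does not rest on it.

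Finally, Protocol 6.8.1 can be read as asking only whether results replicate before and after the switch, which the model does answer. However, Protocol 6.5 and the SAP's rationale both present the analysis as a test of Storyboard itself, which it does not answer.

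**Conclusion.** The point holds as a limit on interpretation. As specified, the interaction estimates a difference between roughly the first month and the later months, and it cannot attribute that difference to Storyboard. If the alert effect fades, the apparent Storyboard effect at the 1.3% planning rate is a ratio of odds ratios of about 0.57 to 0.73, significant in about 11% to 24% of trials. Those figures rest on the assumed fading, on one alert versus control, and on ignoring provider clustering. With no fading there is no bias.

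Two stronger readings are not supported. One is that the SAP's model will in fact credit fatigue to Storyboard; the documents give no rate of decline for these alerts. The other is that the trial's main findings are compromised. The overall randomised contrasts between conditions do not depend on this term and are not affected.

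**What to change.** Report the interaction as first month versus later months of alert availability, and do not describe it as an effect of Storyboard. Apply the same wording to any before/after follow-up under Protocol 6.8.1.

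Add one sensitivity model with time since launch (for example log weeks) and its interaction with condition, keeping the step at 1 November. Give the condition-by-time estimates for the three alerts, so that readers can see whether any effect persists and whether the formats differ. State that the separation of step from trend is partial and depends on the assumed shape of the trend. As the SAP says the analyses are complete, label this model post hoc.

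The cost is one model and a change of wording. The SAP's indicator already depends on encounter timing. The documents do not say that the study team's de-identified file holds encounter dates, so the data broker may need to supply days since launch. The statistical price is a much wider interval for the step, with an SE about 70% larger under log time in the worked case.

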2 ABSTRACT

Cardiovascular disease is the leading cause of death in the United States, with greater than 600,000 people dying annually. The American Academy of Pediatrics began in 2008 with initial recommendations for lipid screening for all at-risk youth between 2-11 years of age. More aggressive guidelines have been recommended since 2011; however, little progress has been made in improving global screening for lipid disease in the pediatric population. This is a randomized controlled study examining provider and patient response to alerts in the electronic health record, to determine the most effective future alert structure to improve provider and patient compliance with evidence-based medicine practices. All pediatric patients between the ages of 9-11 that are seen in a primary care office, CareWorks, cardiology, nutrition, or during an endocrinology visit, their parents/legally authorized guardians, and their attending providers will be eligible for the study. Patients who were already screened or who previously received a diagnosis of familial hypercholesterolemia will be excluded. Patients will be randomized to a delayed-intervention control condition or one of three different alert types (health maintenance tab, best practice alert, or their combination) that their attending providers will receive. Outcomes will include lipid screening orders by providers (yes/no) and screening completions by patients (yes/no) within one week of the orders. The study timeframe will encompass six months of visits from study launch plus final delays in order completion. Analysis will assess which of the conditions results in the highest proportion of orders and completions for pediatric patients across the Geisinger Health System. After the end of the study timeframe, the most effective alert will be implemented for all eligible pediatric patients. We will also be looking exploratorily at 6-month pre-intervention data so we can run a pre-post analysis in addition to our comparison across study arms. This will allow us to assess and adjust for secular changes in screening over time, independent of the alerts.

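### The exploratory pre-post model has no provider-by-period term, so its p-values and confidence intervals may be too optimistic if providers' ordering drifts differently between the two half-years

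*SAP*

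**What the plan says.** The SAP's Primary Analyses section models orders and completions with a binary logistic mixed model, "as a function of condition, with the provider added to the model as a random effect". Its Additional Analyses section then turns to the pre-post comparison, for which "the researchers examined the records of 12,252 eligible patients with the same kind of visits 6 months prior to the study period". The model is carried over: "The four experimental conditions were compared against this pre-alert group using the same kind of GLMM used in the primary analyses". The SAP mentions no provider-by-period effect, random slope for period or cluster-robust standard error. It makes no multiplicity adjustment for these contrasts, and the general threshold is two-tailed p-"values < 0.05 were used to determine statistical significance".

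The protocol's Abstract calls this analysis exploratory but gives it a definite job: "This will allow us to assess and adjust for secular changes in screening over time, independent of the alerts".

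**The concern.** One provider intercept suits the randomised comparisons. Patients are randomised individually at the visit (protocol 6.3 and 6.5), so one provider can see all four arms in the same months, and a change in that provider's habits falls on all arms alike.

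The pre-post contrasts lack this protection. All pre-alert children are in one half-year and all trial children are in the next. A single intercept per provider assumes that every provider's log-odds of ordering moved by the same amount between the two. If some providers take up lipid ordering and others do not, each provider's block of patients moves together in one period, and the model has no variance term for it. A logistic model has no free residual variance to absorb it either, so the drift is simply missing from the standard error.

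The documents make uneven drift plausible. Protocol section 5 says many providers do not know the guideline and that ordering is not part of workflow. The SAP says Storyboard, introduced on 1 November 2019 (about a month into the study by protocol 6.5), might have altered how providers engage with alerts. Providers may also carry over to control patients what alerts for other patients taught them.

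Control versus pre-alert is the contrast that shows secular change. If its standard error is too small, drift in a few busy providers can be declared a system-wide change in screening.

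**Working it through.** **Inputs from the documents.** Pre-alert n = 12,252 (SAP, Additional Analyses). Planned arm size 4,500 (protocol 6.8.2; the achieved size is not given). Two-sided alpha 0.05. Base rate: "if we assume a default screening rate of 1.3"%, from 1,238/96,944 = 1.28%.

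**The plan's own figures.** The documents give no figure for the pre-post model. The sample-size figures in 6.8.2 reproduce:
- d = 0.076 at 95% power: n = 2(1.960 + 1.645)²/0.076² = 4,500 per arm.
- d = 0.20 gives 650 per arm.
- The protocol says 4,500 "allows us to detect a 1% increase in screenings (to 2.3%) with 95% power, using a binomial proportion z-test". The pooled z-test needs 4,591 per arm, and 4,500 gives 94.6% power.
- 1.3% against 4.7% needs 652 per arm.

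**Assumptions not in the documents.** Number of providers K; caseload coefficient of variation (CV) 1; between-provider variance 0.5; provider-by-period variance s² from 0 to 0.5 (logit scale); a 5% rate as a sensitivity case.

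**Step 1: approximate formula.** With pq = 0.013 × 0.987 = 0.01283, the sampling variance of the pre-versus-arm log odds ratio is

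1/(12,252 × 0.01283) + 1/(4,500 × 0.01283) = 0.00636 + 0.01732 = 0.02368, so SE = 0.154.

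Independent provider-by-period drift adds 2s²(1 + CV²)/K. The single-intercept model leaves this out, so the actual type I error is 2Φ(−1.96 × model SE / true SD).

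| K | s² | Added variance | True SD | Type I error |
|---|---|---|---|---|
| 600 | 0.10 | 0.0007 | 0.156 | 5.3% |
| 600 | 0.25 | 0.0017 | 0.159 | 5.8% |
| 300 | 0.25 | 0.0033 | 0.164 | 6.7% |
| 100 | 0.25 | 0.0100 | 0.184 | 10.0% |

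**Step 2: simulation.** No average pre-post change; 1,000 to 2,000 runs per scenario; maximum-likelihood logistic mixed models. Type I error of one pre-versus-arm contrast at a 1.3% rate:

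| K | s² | Provider intercept only | Plus provider-by-period |
|---|---|---|---|
| 300 | 0 | 5.8% | 5.4% |
| 300 | 0.10 | 6.4% | 5.7% |
| 300 | 0.25 | 8.8% | 5.8% |
| 300 | 0.50 | 10.7% | 5.2% |
| 100 | 0 | 4.5% | 4.2% |
| 100 | 0.10 | 7.2% | 4.9% |
| 100 | 0.25 | 11.9% | 4.2% |
| 100 | 0.50 | 20.0% | 5.0% |
| 50 | 0.25 | 19.1% | 6.5% |
| 50 | 0.50 | 29.0% | 8.3% |

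For K = 100 and s² = 0.25, the single-intercept model reports a mean SE of 0.157 against an actual SD of 0.197, and interval coverage is 88%; with the added term coverage is 96%. With 3,063 per arm (12,252/4) instead of 4,500, the same scenario gives 12.3% and 5.4%.

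At an assumed 5% rate with s² = 0.25, the error is 25.1% (K = 100) and 15.7% (K = 300), falling to 6.5% and 5.6% with the added term.

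The formula runs somewhat below the simulation (10.0% against 11.9%; 6.7% against 8.8%). The 600-provider figures come from the formula only and may be slightly low.

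**Step 3: the randomised contrasts.** In the same simulated data, arm-versus-arm comparisons under the single-intercept model stay at 4.4% to 6.8%.

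**The case against.** A reader might infer that the pre-post p-values and intervals are too optimistic as a matter of fact. The documents do not support that. It requires drift that differs between providers, and the documents report no such variance, no provider count and no caseloads. The study takes in primary care, CareWorks, cardiology, endocrinology and nutrition clinics, so several hundred providers is as tenable as one hundred. With no drift the SAP's model is sound. The largest error rates above need few providers, large drift or a 5% rate that the documents do not state. All of this stands, and it makes the point conditional.

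The single shared intercept is also inferred. The SAP says that provider is a random effect and does not spell out the structure. That stands too, and it is a reason to state the structure.

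A deeper objection is about the target. If busy providers in this health system really did change their ordering, screening in the system really did change, and detecting that is arguably what the protocol wants. This has force if the aim is only to describe these providers in these two half-years. But the protocol means to use the contrast to infer secular change apart from the alerts and to adjust for it. For that use, idiosyncratic movement by a few providers is a source of uncertainty that belongs in the interval.

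Finally, the analysis is exploratory, and the choice of alert rests on the comparison across conditions. This limits the consequences but does not argue against a cheap correction.

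**Conclusion.** The point holds in conditional form. The pre-post model, as described, has no term for provider-specific change between half-years, and its standard errors are too small to the extent that such change exists.

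At the protocol's 1.3% rate, the type I error of one contrast runs from about 5% (no drift, or about 600 providers with s² of 0.1 to 0.25) to about 9% to 12% (300 to 100 providers, s² = 0.25). It goes further with fewer providers, larger drift or a higher rate. These sizes rest on assumed provider counts, caseloads and variances and on the planned arm size. The direction does not.

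Two wider inferences are not supported. The concurrent randomised contrasts are not undermined. Nor would this correction make the before-after comparison unconfounded, because a change shared by all providers would remain.

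**What to change.** In the SAP's pre-post paragraph, replace the reference back to the primary model with an explicit one: a binary logistic mixed model with condition as fixed effect, a random intercept for provider, and a random intercept for provider-by-period (pre-alert half-year versus trial half-year). Report the pre-post odds ratios and confidence intervals from this model, with the number of providers and the estimated variance components. Leave the primary model unchanged.

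The SAP says the analyses are already complete, so the cost is refitting one exploratory model on data in hand and adding a sentence to the SAP. The downside is wider exploratory intervals if drift is real, and a possible zero-variance fit if it is not, in which case the model reduces to the current one.

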6 STUDY DESIGN

6.1 Description

This study will be a randomized, prospective study in which patients of ages 9 to 11 who are seen within a primary care, CareWorks, cardiology, endocrinology, or nutrition clinic within our health system will be randomized 1:1 to one of four groups. Based on the group to which the patient is randomized, the provider seeing that patient will receive either no alert (control group, described below) or one of three electronic medical record alerts regarding the need for a non-fasting lipid panel for that patient:

- Best practice alert (BPA)
- Health maintenance tab (HMT)
- Both BPA and HMT

Providers of patients randomized to the control group will not receive a BPA or HMT, which reflects the current standard care process.

There will also be a 6-month pre-intervention data pull completed so we can run a pre-post analysis in addition to our comparison across study arms.

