6.2 Study Population

6.2.1 Approximate Number of Subjects

We plan to enroll all eligible pediatric participants in this study (see inclusion and exclusion criteria, below). In a recent six-month period, according to Slicer Dicer, there were 7,906 established and new well child visit for 11-year-olds in the Geisinger system. Assuming similar population levels for 9- and 10-year-olds, we expect to enroll into our study approximately 24,000 pediatric participants as well as their parents/LARs and providers during our six-month enrollment period. However, we will enroll into the study all eligible participants who present at qualifying Geisinger sites during that period. Additionally, for exploratory analysis, we will enroll 21,000 pediatric participants from the six-month period just preceding the intervention, using the same inclusion criteria as below.

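### The SAP's only stated reason for not adjusting the exploratory pre-post contrasts, a shared comparison group, is invalid; at the planned arm size the family-wise error is about 13.7% (three alert arms) or 17.6% (all four contrasts)

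*SAP*

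**What the plan says.** The last paragraph of the SAP (Additional Analyses) describes the pre-post comparison. The pre-alert group is fixed in size: "the researchers examined the records of 12,252 eligible patients". The contrasts are then defined: "The four experimental conditions were compared against this pre-alert group using the same kind of GLMM used in the primary analyses". The paragraph closes with the multiplicity statement: "All of the contrasts were made against one group, the pre-alert group, so no adjustment was made for multiple comparisons".

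No significance threshold is restated there. The one in the SAP's Primary Analyses section is "two-tailed p -values < 0.05 were used to determine statistical significance", and it carries over because the pre-post models are said to be of the same kind.

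The protocol calls this analysis exploratory in its Abstract (section 2) and again in section 6.2.1: "for exploratory analysis, we will enroll 21,000 pediatric participants from the six-month period just preceding the intervention". The Abstract also gives its purpose, which is to assess and adjust for changes in screening over time that have nothing to do with the alerts. The protocol specifies no multiplicity correction for any analysis.

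**The concern.** The word linking the two halves of the SAP sentence makes the shared group the reason for not adjusting, and no other reason is given. Comparing several arms with one common group is the many-to-one setting for which Dunnett's procedure was devised, so the feature cited as removing the problem is the one that defines it.

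The sentence also treats four contrasts alike although they answer two questions. Control versus pre-alert involves no alert and is the check for secular drift. The other three ask whether screening under an alert differs from the earlier period.

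At stake is how far a reader can trust a significant pre-post result for an alert arm. With no true change, at least one such result would appear more often than the nominal 5%, while the SAP tells the reader that the design makes correction unnecessary.

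**Working it through.** **Inputs**

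- Two-sided 0.05 per contrast (SAP, Primary Analyses; carried over).
- Four contrasts per outcome, three of them alert arms (SAP, Additional Analyses).
- Pre-alert group of 12,252 (SAP). The protocol's planned 21,000 (6.2.1) serves as a sensitivity value.
- Arm size: "Randomly allocated at 4,500 patients per condition" (Protocol 6.8.2), equal across arms because patients "will be randomized 1:1 to one of four groups" (6.1). As an alternative, "we expect to enroll into our study approximately 24,000 pediatric participants" (6.2.1), which is 24,000/4 = 6,000 per arm. Neither document gives achieved arm sizes.

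**Step 1: the plan's own figure.** The documents state no family-wise error. They do state 95% power for d = 0.076 at 4,500 per condition: 0.076 × √(4,500/2) = 3.605; 3.605 − 1.960 = 1.645; Φ(1.645) = 0.950. This reproduces.

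**Step 2: correlation from the shared group.** Two contrasts against one group of size n₀, with n per arm and equal rates, have correlation ρ = (1/n₀)/(1/n + 1/n₀) = n/(n + n₀). Here ρ = 4,500/16,752 = 0.269.

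**Step 3: family-wise error with all k nulls true.** With c = 1.96,

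FWER = 1 − ∫ φ(u) [Φ((c − √ρ·u)/√(1−ρ)) − Φ((−c − √ρ·u)/√(1−ρ))]^k du.

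| Per arm | Pre-alert | ρ | k = 3 | k = 4 |
|---|---|---|---|---|
| 3,000 (assumed) | 12,252 | 0.197 | 14.0% | 18.0% |
| 4,500 | 12,252 | 0.269 | 13.7% | 17.6% |
| 6,000 | 12,252 | 0.329 | 13.5% | 17.2% |
| 4,500 | 21,000 | 0.176 | 14.0% | 18.1% |

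At 4,500 versus 12,252, two true nulls give 9.6% and one gives 5%.

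**Step 4: limits that do not need arm sizes.** Under independence, 1 − 0.95³ = 14.3% and 1 − 0.95⁴ = 18.5%. The Bonferroni bounds are 15% and 20%.

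**Step 5: simulation check.** Binomial draws at 1.3% in every group, 4,500 per arm versus 12,252, 400,000 runs, pooled z-test: 13.6% (three) and 17.5% (four).

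**Step 6: what control would require.** Setting the Step 3 expression to 5% and solving for c gives a single-step Dunnett critical value of 2.378 for three contrasts (p about 0.017) and 2.478 for four. The ratio 2.378/1.96 = 1.213 makes intervals about 21% wider on the log-odds scale. At 1.3% in both groups the standard error of the log odds ratio is 0.154, so the limits move from the estimate times or divided by 1.35 to times or divided by 1.44.

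**Step 7: how often adjustment would change a verdict.** This is the probability that z for one alert contrast lies between 1.96 and 2.378. At the planned 1.3% versus 2.3% (Protocol 6.8.2), the expected z is 4.56 (log odds ratio) or 4.07 (risk difference), giving 1.0% or 2.8%. At true rates of 1.7% or 1.8% it is about 16% on the log-odds scale.

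**The case against.** The strongest reply is that the decision not to adjust is defensible and only the explanation is poor. The protocol twice calls the analysis exploratory, the SAP places it apart from the primary analyses, and the SAP says its own protocol section was dropped as redundant, so the two documents are meant to be read together. This stands, and it keeps the matter minor. It does not rescue the sentence, because the SAP neither applies the exploratory label to these contrasts nor relies on it.

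Second, the primary pairwise tests use least significant difference, which leaves each comparison at 0.05. Using Dunnett or Holm here would hold an exploratory, non-randomised analysis to a stricter standard than the randomised one. That is a fair reason to prefer the labelling route.

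Third, the 16% in Step 7 is close to the most any trial could show: a unit-variance z falls between 1.96 and 2.378 with probability at most 2Φ(0.209) − 1 = 16.6%. It marks where adjustment matters most and is not a forecast for this study.

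Fourth, the documents define no family, so choosing three or four contrasts is a judgement. Both figures are therefore shown.

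A reader might infer that 13.7% and 17.6% are ceilings. They are not: they depend on a planned arm size, and smaller arms give more. A reader might also infer a conflict with the protocol over multiplicity. None is shown, since the protocol specifies no correction.

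**Conclusion.** The stated rationale is wrong as written. At the planned 4,500 per arm against 12,252, family-wise error per outcome is about 13.7% for the three alert-arm contrasts and 17.6% for all four, with independence limits of 14.3% and 18.5%. No arm size in the range examined brings it near 5%.

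These figures assume that all nulls in the family are true, that the 0.05 threshold carries over, that large-sample normality holds, and that the provider random effect can be ignored. That effect may change the correlation, and the documents give no intraclass correlation. Over ρ from 0 to 0.5 the error runs from 14.3% to 12.5% (three) and from 18.5% to 15.6% (four).

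Severity is minor. It would be tempting to conclude that the trial's main findings or the choice of alert for roll-out are compromised. The documents do not support that: the randomised comparisons do not use the pre-alert group. Nor would a multiplicity correction deal with season or case mix, which are separate limits of a before-after comparison.

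**What to change.** Delete the closing sentence of the SAP and replace it with wording such as: *These pre-post contrasts are exploratory and non-randomised; unadjusted estimates and 95% intervals are reported under that label, without claims of significance.* If that is followed, nothing need be recalculated.

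If significance is to be claimed for an alert arm versus pre-alert, name one method over the three alert-arm contrasts per outcome: single-step Dunnett (critical value about 2.38 at the planned sizes) or Holm (0.0167, 0.025, 0.05 in sequence). Keep control versus pre-alert separate as the secular-trend check. State that the method was chosen after the analyses were completed, as the SAP says they were.

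**Cost.** One sentence, or a recalculation from models already fitted, with no new data. Dunnett intervals would be about 21% wider, and the approach would be stricter than the least significant difference tests used for the primary comparisons. Keeping the control contrast outside the family protects the drift check: a rise from 1.3% to about 1.9%, detectable with 80% power unadjusted, would have about 63% power at the four-contrast value of 2.478. Any method adopted now remains post hoc.
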